1.3 Role of FDG-PET/CT in FNAC-indeterminate thyroid nodules

In 2006, our group published a prospective study on the results of FDG-PET in 44 patients with FNAC-indeterminate thyroid nodules. We described a positive and negative predictive value for malignancy of 32% and 100%, respectively (prevalence: 14%) [10]. As our findings were supported by several other studies [11-15], all with similar negative predictive values but

varying positive predictive values, we performed a systematic review and meta-analysis of the literature [4]. The prevalence of benign disease, histologically determined in all these patients after resection, was 74%. In all these patients, FDG-PET/CT was performed prior to surgery on previous generation PET/CT-scanners. Only 3 out of 83 patients with a negative FDG-PET and 55 out of 142 patients with a positive scan showed a malignancy at diagnostic surgery (negative and positive predictive value: 96% and 39%, respectively. The sensitivity of FDG-PET/CT was strongly related to the size of the TN, due to limited spatial resolution of the PET(/CT) scanners used. Due to the limited specificity of the FDG-PET/CT for malignancy, the positive predictive value was found to be poor (Appendix IV: Performance of FDG-PET/CT in indeterminate thyroid nodules, §15.4, p92). Very recently, these data were confirmed by a prospective series of 46 patents with FNAC (non-oncocytic) follicular lesions (Bethesda category III and IV) larger than 20 mm (DTC prevalence: 28%) with a negative and positive predictive value of 61% and 94%, respectively [16]. The authors state that FDG-PET/CT could reduce the number of diagnostic (hemi)thyroidectomies by 13-25%.

Based on the high sensitivity of FDG-PET/CT to detect malignancy in FNAC-indeterminate thyroid nodules, we postulate that incorporation of this imaging modality in the diagnostic workup of these nodules could decrease the prevalence of benign nodules at the time of diagnostic hemithyroidectomy from 74% to 39%. Due to the limited specificity of FDG-PET/CT, still 61% of operated patients will be diagnosed with a benign disorder (i.e. patients with false-positive FDG-PET/CT), being 74% prior to the inclusion of FDG-PET. Although this seems a moderate improvement, the number of hemithyroidectomies for FNAC-indeterminate nodules is reduced by 37%. We therefore consider this modality potentially valuable tool in this category of patients.

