We have described a false-negative ratio of FDG-PET/CT in ~1.3% of all patients, which is within the range of the a priori risk of DTC in any thyroid nodule (<5%). Sensitivity is highly dependent of nodule size due to the earlier mentioned effect of limited spatial resolution of a PET-scanner (5-8 mm FWHM on PET/CT-scanners from the meta-analysis, 3-4 mm for current time-of-flight PET/CT-scanners). This false-negative ratio could delay treatment for thyroid malignancy, but the consequences are considered to be minimal, due to the relative indolent course of this disease. Furthermore, there is limited impact on survival upon the transition from localised (stage I) to regional (stage II) disease (5-year overall survival for both groups is 100%), all with good (curative) treatment options [5].

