8.4.1 Specific criteria for withdrawal (at the end of the study)

The false-negative FDG-PET/CT ratio is expected to be around 1.3%, but we accept a falsenegative ratio of up to 5% (i.e. the a priori risk of malignancy in any thyroid nodule). After

EFFECTS

inclusion and surgery of all 44 patients in the control study-arm, final analysis will be performed. In case 6 or more of all these 44 patients (π_1 *=13.6%) in the control study-arm have a false-negative FDG-PET/CT, the treating physicians of all PET-negative patients from the experimental study arm will be advised to proceed to diagnostic (hemi)thyroidectomy. This number is based on the cumulative binomial distribution, by solving:

$$\sum_{n=X}^{n=N} \binom{N}{X} \cdot p^X \cdot (1-p)^{N-X} \le \alpha$$

With N=44, p=0.05 and α =0.025 (Bonferroni-adjusted), resulting in X≥6. Single-sided testing was used. Figure 7, p57.

[figure not shown]

Figure 7: Cumulative Binomial Distribution for a sample size of 22 (interim-analysis) or 44 (end-of-study evaluation) for an individual patient probability of a false-negative FDG-PET/CT of 0.05. In case that more than 4/22 patients (18.2%) at time of the interim analysis or 6/44 (13.6%) patients at time of the end-of-study evaluation have a false-positive FDG-PET/CT (in the control study arm), the false-negative probability is larger than the maximum accepted value of 0.05.

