8.7 Premature termination of the study (interim-analysis)

The false-negative FDG-PET/CT ratio is expected to be around 1.3%, but we accept a falsenegative ratio of up to 5% (i.e. the a priori risk of malignancy in any thyroid nodule). After inclusion and surgery of 22 (50%) patients in the control study-arm, an interim analysis will be performed by the safety committee (§9.5: Data Safety Monitoring Board (DSMB) / Safety Committee, p62). In case 4 or more of these first 22 patients (π_1 *=18.2%) in the control studyarm have a false-negative FDG-PET/CT, the study will be terminated preliminarily and the physicians of all PET-negative patients in the experimental study arm will be informed to advise them to undergo diagnostic (hemi)thyroidectomy. This number is based on the cumulative binomial distribution, by solving:

$$\sum_{n=X}^{n=N} \binom{N}{X} \cdot p^X \cdot (1-p)^{N-X} \leq \alpha$$

With N=22, p=0.05 and α =0.025 (Bonferroni-adjusted), resulting in X≥4. Single-sided testing was used. Figure 7, p57.

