8.8 Mid- to long-term follow-up

The duration of short-term follow-up since FDG-PET/CT for this study is set at 12 months, as it is expected that most treatment procedures have taken place within this period and most complications have been resolved. Primary and secondary outcome measures are therefore collected during this one-year period.

In the ideal case that no false-negative FDG-PET/CT-scans occur, it is safe to assume that recurrences and other mid- to long-term sequelae would occur in same fractions in both study arms. However, a one-year follow-up period could be considered too short to conclude a false-negative-fraction for FDG-PET/CT as a delayed diagnosis of malignancy might be made over a year after initial FNAC as DTC usually follows an indolent growth. Also, the costs and utilities (health related quality of life) attributed to delayed treatment would not be completely incorporated in the study most likely leading to an underestimation of false-negative rates, an underestimation of costs, and an overestimation of utility in de experimental study arm due to censoring.

Therefore, five year after the inclusion of the last patient a retrospective study will be conducted using patient files completed with contact with the general practitioners of these patients to investigate the mid- to long-term effects of our intervention.

All treating physicians are aware that about 3.6% of all negative FDG-PET/CT scans are falsenegative (1.3% of all patients included in the study). The short-term follow-up will distinguish a portion of these patients with thyroid malignancy, but probably not all. Therefore, the treating physicians are advised to follow-up the nodules for at least 5 years like "benign nodules" in the ATA-guidelines [6], recommendation 14:

- (a) It is recommended that all benign thyroid nodules be followed with serial US examinations 6–18 months after the initial FNAB. If nodule size is stable (i.e., no more than a 50% change in volume or <20% increase in at least two nodule dimensions in solid nodules or in the solid portion of mixed cystic–solid nodules), the interval before the next follow-up clinical examination or US may be longer, e.g., every 3–5 years.

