An effect on the individual is not predictable. About 3.6% of all negative FDG-PET/CTs are expected to false-negative (~1.3% of all patients: Appendix IV: Performance of FDG-PET/CT in indeterminate thyroid nodules, §15.4, p92.

j. Can effects be managed?

Yes, both due to the confirmatory US and the analyses on the control study arm we expect to be able to keep the number of patients with thyroid malignancies who will not get surgery within a year below 5% (i.e. similar to the risk of malignancy in any thyroid nodule which did not have FNAC).

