13.2 Synthesis

The measures that have been taken to reduce the risk are:

- Exclusion of patients with a very high prior risk on thyroid malignancy,
- Exclude patients with potential false-negative FDG-PET/CT scans (e.g. hyperglycaemia, deregulated diabetes mellitus),
- Exclude patients with FDG-PET/CT scans which will be very difficult to interpret (e.g. multinodular goitre without dominant node, obvious infection to the neck),
- Optimised PET-acquisition with administered doses as low as reasonably achievable, limiting the investigated body area and increasing the speed of clearance of the radiopharmaceutical by forced diuresis,
- Exclusion of patient with highest amount of effective dose contributed to ionising radiation and highest amount of detriment (i.e. minors),
- Prevention of (irrelevant) incidental PET findings leading to (invasive and costly) diagnostic procedures by scanning only the head, neck and thoracic inlet,
- Centralised, double-reading of the FDG-PET/CT,
- Centralised, revision of cytological material (if definite benign or (suspicious of) malignancy, patients will be excluded from the study (i.e. not indeterminate FNAC) and treated accordingly,
- Confirmatory US in FDG-PET/CT-negative patients in the experimental study-arm,
- Interim en end-of-study analysis on the control study arm to verify that the FDG-PET/CT false negative will not exceed 5% by an independent board (safety committee §9.5: Data Safety Monitoring Board (DSMB) / Safety Committee, p62) consisting of a statistician, clinician and medical imager.
- Planned long-term follow-up to prevent an underestimation of the false-negative fraction of PET due to the indolent nature of the disease.
- In case explorative genetic testing shows mutations specific for malignancy (i.e. BRAF, TERT) but the patient did not undergo surgery (i.e. false-negative PET in the experimental arm), the treating physician will be informed of this (unexpected) finding.

Based on the recommendation of the European Science Foundation risk is classified according to Table 12, p84:

Amount of Injury:	Negligible:	Moderate:	Severe:	
Probability:				
Low	Negligible risk	Negligible risk	Moderate risk	
Intermediate	Negligible risk	Moderate risk	High risk	
High	Moderate risk	High risk	High risk	

Table 12: Risk classification in relation to the probability and severity of potential injury.

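### The 5% false-negative limit is borrowed from the cancer risk of one nodule but tested over all controls, where it corresponds to about 13.6% of PET-negative nodules

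*Protocol*

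**What the plan says.** Section 8.7 sets the accepted ratio at up to "5% (i.e. the a priori risk of malignancy in any thyroid nodule"), against an expected 1.3%. The interim rule is "In case 4 or more of these first 22 patients" with a false-negative scan. Section 8.4.1 repeats the limit at the end of the study: "In case 6 or more of all these 44 patients". Both come from a one-sided binomial test with p=0.05 and α=0.025. When the final rule is met, physicians of the PET-negative patients in the experimental arm are advised to proceed to surgery.

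Section 1.3 makes the same comparison: the 1.3% of all patients is called "within the range of the a priori risk of DTC in any thyroid nodule (<5"%). The same section gives the other denominator, "Only 3 out of 83 patients with a negative FDG-PET" having a malignancy. Section 8.8 states that "about 3.6% of all negative FDG-PET/CT scans are" false-negative, and uses that scale when it compares with Bethesda I and II risks.

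Two assurances follow. Section 13.1.2j says "we expect to be able to keep the number of patients with thyroid malignancies who will not get surgery within a year below 5"%, again likened to the risk of malignancy in any nodule. Section 13.2 lists the control-arm analyses as a means "to verify that the FDG-PET/CT false negative will not exceed 5"%. Section 4.4 adds that 88 experimental-arm patients should establish a false-negative rate of at most 7.5%.

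**The concern.** The cancer risk of a nodule is a risk per nodule left in place. Its counterpart here is the risk of cancer in a nodule left unoperated after a negative scan, expected at 3.6%. The rule instead divides by all controls. PET-positive controls cannot be false negatives, so they only enlarge the denominator. Setting 1.3% beside 5% suggests almost a fourfold margin; on matching scales it is 3.6% beside 5%.

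This is the only formal statistical trigger on the false-negative rate, and the end-of-study look was still ahead at the February 2019 addendum. At stake is how much reassurance a result below 6/44 gives about the patients whose surgery was cancelled. The primary comparison of unbeneficial treatment is not affected.

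**Working it through.** **Inputs.** Limit 5%, one-sided α 0.025, N=22 and N=44 (8.7, 8.4.1). PET-negative share 83/225 = 0.369, with 3 cancers among the 83 (1.3, Appendix IV). Section 11.4 expects about 35-40% PET-negative, and the 55-patient series in section 1.5 had 45%. Pooled NPV 96.4%, interval 89.9-99.2% (Appendix IV).

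**1. The plan's cut-offs reproduce.** For X ~ Bin(N, 0.05):
- N=22: P(X≥3)=0.095, P(X≥4)=0.0222, so 4.
- N=44: P(X≥5)=0.067, P(X≥6)=0.0216, so 6.

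**2. Conversion of the limit.** Rate per PET-negative = rate over all patients / PET-negative share.
- Share 83/225: 0.05/0.369 = 0.136.
- Share 35%: 0.143. Share 40%: 0.125. Share 45%: 0.111.

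This 13.6% agrees with 6/44 = 13.6% by coincidence only. Six false negatives in 44 controls means 6 among about 44 × 0.369 = 16 PET-negative controls.

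**3. How often the final rule fires.** P(X≥6) for X ~ Bin(44, r × share), where r is the true cancer risk per PET-negative nodule:

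| r | share 35% | share 83/225 | share 45% |
|---|---|---|---|
| 5% | 0.0001 | 0.0002 | 0.0004 |
| 10% | 0.004 | 0.005 | 0.014 |
| 20% | 0.08 | 0.10 | 0.20 |

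Over both looks, at share 83/225, the probability is 0.011 at r=10% and 0.13 at r=20%.

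**4. Which values of r the protocol supports.** The pooled NPV interval puts r between 0.8% and 10.1% (100 minus 99.2 and 89.9), so 10% is about its upper end. The section 1.5 series had 5 false negatives in 25 negative scans (20%), but three were of uncertain malignant potential. Malignancies alone were 2/25 (8%).

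**5. What a clean result would show.** Exact upper 97.5% limit for zero events: 1 − 0.025^(1/n).
- 0/44: 8.0% of all patients.
- 0/16: 20.6% of PET-negatives.

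Both exceed 5%, so no possible control-arm result can show that the rate is below 5%.

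**6. The same formula on PET-negative controls.** With p=0.05 and α=0.025, the cut-off is 4 for any n from 14 to 22 (for n=16, P(X≥3)=0.043 and P(X≥4)=0.007). With n ~ Bin(44, 83/225) and the cut-off solved for each n, the comparison is met with probability 0.011 at r=5%, 0.09 at 10% and 0.45 at 20%.

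**7. The 7.5% sentence in 4.4.** P(X≥5 | 88, 3/225)=0.0066 and P(X≥5 | 88, 0.075)=0.798. These match the printed α and power. They describe rejecting 1.3% when the truth is 7.5%, and do not set a maximum of 7.5%.

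**The case against.** The rule tests the quantity it declares. The expected 1.3%, the 5% limit and both cut-offs are per patient, and 13.1.2j states the aim as a proportion of patients. On that scale a true 10% per PET-negative nodule is 3.7% of patients (0.10 × 0.369), inside the accepted limit, so a firing probability of 0.005 is correct behaviour. This stands. It does not supply a reason for taking the limit from a per-nodule risk, which 13.1.2j repeats.

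Section 13.1.2e says action follows if the rate significantly exceeds 5%, which describes the test correctly. The overclaim is therefore mainly the verb in 13.2, together with the separate sentence in 4.4.

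The per-negative figure is also not hidden. Section 8.8 says treating physicians know the 3.6%; NPV and exact limits are planned (10.2, 10.3); and the Safety Committee may suggest further analyses. Individual patients are further protected by the 12-month ultrasound, disclosure of worrying genetic results and 5-year follow-up.

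A reader might infer that a 20% risk per PET-negative nodule is a realistic prospect. The documents do not support that. The figure needs lesions of uncertain malignant potential counted as false negatives. Section 8.3.4 does count them so for scan classification, but it also calls them strictly benign, and the 5% benchmark concerns malignancy. The 20% row is a stress case.

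A reader might also infer that the Safety Committee would never see the PET-negative rate. Its charter is not among the documents, so that cannot be established.

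**Conclusion.** The point holds as a mismatch between the justification of the limit and its denominator, and as an overstated assurance in 13.2. Five percent of all patients is about 13.6% per PET-negative nodule, given the 83/225 share from the protocol's meta-analysis (about 11-14% for 45-35%). At about the upper end of the protocol's pooled interval the final rule would almost never fire (0.005). With 44 controls, no result can verify a rate below 5% on either scale.

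Two stronger readings should be resisted. The cut-offs are not miscalculated; they follow exactly from their stated inputs. Nor does the protocol anywhere declare a tolerance of 13.6%; that is a conversion and moves with the PET-negative share.

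**What to change.** Keep 6/44 as the binding rule and make these changes:

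- **End-of-study look.** Also give the Safety Committee cancers divided by PET-negative controls (1 − NPV) with the Clopper-Pearson interval, shown with and without NIFTP and the lesions of uncertain malignant potential, as advisory information. State that 4 or more, for 14 to 22 PET-negative controls, prompts a documented committee recommendation even if 6/44 is not met. This case must be covered: with 16 PET-negative controls and a true 20%, the chance of 4 or 5 cancers is about 0.32.
- **8.4.1 and 8.7.** State that 5% of all patients is about 13.6% of PET-negatives at the 83/225 share.
- **13.2.** Say that the analyses serve to detect whether the rate significantly exceeds 5%, in line with 13.1.2e.
- **4.4.** Restate the 7.5% sentence as about 80% power to reject 1.3% if the true rate is 7.5%.

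No new data are needed, and the estimate and interval are already planned. The cost is an amendment notified to the METC, a false-alarm chance of about 0.01 at a true 5%, and a weaker stated assurance. The gain is limited: the advisory comparison is met with probability only 0.09 at a true 10%, so the interval will tell the committee more than the count.

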8.5 Replacement of individual subjects after withdrawal

In case of secondary exclusion (e.g. based on central cytology revision), new patients can be entered into the study to a maximum of 15% (20 patients). This limit is set to the same value as the amount of maximum data-attrition for budgetary reasons.

Once a PET-scan has been performed, replacement is not possible. Sample size adjustments have been made for data-attrition (e.g. a patient is lost during follow-up). In case a patient cannot adhere to the protocol during any phase of the study (e.g. is considered inoperable or wishes thyroid surgery despite a negative PET-scan in the experimental arm), the reason is

noted, but patients do not switch study arm (i.e. intention-to-treat analysis and not per-protocol analysis).

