4.4 Sample size calculation

Based on the main objective, it is expected that FDG-PET/CT can reduce unjust treatment from ~73.1% (=136/186 benign lesions >10mm) to ~40.3% (=75/186 false-positive and false-negative lesions >10mm, §1.3, p19). Using G*Power version 3.1.9.2. (and validated using JMP from SAS version 9.0.1, STATA version 12.0SE and PASS version 2011), we computed using an α error probability of 0.025 (=0.05/2, Bonferroni correction for interim analysis) a power of 0.80 and an allocation ratio of N_A:N_B=2:1, we need to include at least 90 patients in total (one-tailed test) to establish this difference (60+30 patients in arm A and B respectively).

Since around 82.7% (=186/225, §1.3, p19) fulfil the size criterion, at least 111 patients (74+37 patients in arm A and B respectively) need to be included. Accounting for additional 15% data loss at the final end-point, 132 patients should be included (88+44 patients in arm A and B respectively) (Figure 2, p40).

This total number of patients could at best (assuming no data loss) discern a reduction of 26.6% unjust treatment in the whole population with an actual α error probability of 0.016 and a power of 0.80. This is based on a reduction from 74.2% (prevalence of benign disease in all 225 patients) to 47.6%. In the experimental arm (88 patients), where the number of false-negative PET is estimated to be ~1.3% (3/225), this number of patients should establish a false-negative rate of maximal 7.5% (actual α error probability of 0.0066 and a power of 0.80). All analyses will be performed according to the intention-to-treat principle, meaning that analysis is based on the initial study-arm allocation and not on the treatment eventually received (e.g. a FDG-PET/CT negative patient in the experimental arm does not refrain from surgery and therefore actually is treated according to the control study arm).

[figure not shown]

Figure 2: Relation between study size (N), study-arm size sizes (n₁ and n₂) and effect size. Empirical relation: N=16.33935*ES^{-1.86986}, R²=.999443). Expected ES=73.1%-40.3%=32.8%

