8.6 Follow-up of subjects withdrawn from treatment

All patient files will be examined 12 months and ~5 years after inclusion (§8.8, p58)

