10. STATISTICAL ANALYSIS

10.1 General remarks

All (statistical and economical) analyses will be supported by epidemiologists and biostatisticians from the LUMC.

All continuous data (e.g. age, FDG-PET/CT standardised uptake level (SUV), volumes of care, hospitalisation and sick leave days, Tg-level, questionnaire scores, etc.) will be assessed for (log)normality.

All categorical data (e.g. sex, FDG-PET/CT positive or negative, malignant or benign, histology, etc.) are treated as either ordinal or nominal.

One year is defined as 365.242199 days. Age, overall survival, disease-free-survival are computed with respect to the date of the (last) US guided FNAC that led to study enrolment. Survival is computed, using the Kaplan-Meier method, taking into account censored data (censored to the date of last follow-up or death (for all but overall survival)). For comparison of Kaplan-Meier estimates, the logrank statistic will be used (as the Breslow and Tarone-Ware tests are better used when the data does not fulfil the proportional hazards assumption; they are both weighted versions of the logrank test giving extra weight to events happening earlier on. The Tarone-Ware has slightly less extreme weightings. Both should be avoided in case of a high level of censoring or unequal censoring between groups).

All prices will be calculated based on national price levels (in Euro, €), indexed to the year of first patient inclusion (2015). Price-index-numbers will be used to account for price changes during the years of patient inclusion and follow-up. In case of costs distributed over several years, net present values are computed using a constant 4% discount rate and effects using a constant 1.5% discount rate, which is a common method in the Netherlands (other countries usually use uniform discounting). For all computations, the methods for cost-research of Hakkaart-vanRoijen et al.[68] will be used.

Missing values will not be completed by any means (e.g. average). In case of missing values, the fraction missing values will be stated. Multivariate analysis might therefore only be performed on a subset of patients (without missing values in all independent parameters), however due to the nature of the important independent parameters, we expect that this "subset" of patients will be over 95% of the study population.

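### The rule that missing values are never completed makes the intention-to-treat primary comparison a complete-case one, and the resulting loss is not neutral between the arms

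*Protocol*

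**What the plan says.** Section 8.1.1 defines the primary endpoint as the fraction with unbeneficial treatment, by intention-to-treat: an operation for a benign nodule, or observation of a malignant one. Section 10.1 repeats that all analyses follow intention-to-treat. The same section says "Missing values will not be completed by any means (e.g. average") and adds only that the fraction missing will be reported.

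Under Section 3 the reference standard is histology for operated patients and otherwise 12 months of follow-up including ultrasound. Section 8.3.2 and Table 2 give the 12-month study ultrasound only to PET-negative patients in arm A.

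Section 4.4 allows for 15% data loss, spread equally: 74 to 88 in arm A and 37 to 44 in arm B. Section 8.5 refers back to this with "Sample size adjustments have been made for data-attrition", and its example is a patient lost during follow-up.

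Two other passages bear on a patient without a verified endpoint. Section 8.3.4 calls a nodule malignant if malignancy is diagnosed at its location and treats every other nodule as benign. Section 8.6 says of withdrawn subjects: "All patient files will be examined 12 months and ~5 years after inclusion". Nothing says which of these rules governs the primary endpoint.

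**The concern.** Inflating the sample replaces patients lost at random. It does not restore an effect when the lost patients differ in outcome from those who remain and sit mainly in one arm.

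A patient operated as planned has an endpoint soon after surgery. A PET-negative patient in arm A must wait a year, so loss during follow-up falls mainly there, and these patients are nearly all successes of the PET strategy. Leaving them out raises the arm A failure rate.

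The control arm has its own route. Section 8.5 mentions patients found inoperable, Section 8.3.5 patients who choose not to have surgery, and Section 8.4 withdrawal at any time. A control patient who is not operated has neither histology nor a study ultrasound. If benign, that patient is a success by the endpoint definition. Leaving such patients out raises the control failure rate and enlarges the apparent effect.

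The size and even the direction of the bias therefore depend on a mix of losses that nobody has planned. A later choice between dropping and classifying these patients could move the primary estimate by several points.

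**Working it through.** **Inputs**
- Section 4.4: one-sided α 0.025, "a power of 0.80 and an allocation ratio of N_A:N_B=2:1"; failure rates for nodules >10 mm of 136/186 = 73.1% (control) and 75/186 = 40.3% (PET-driven); size share 186/225; 15% loss.
- Section 1.3 and Appendix IV: 83 PET-negatives, 3 of them malignant.
- Section 3: about 32 unoperated patients expected among the 88 in arm A.

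**The plan's own figures**
- Exact power of the one-sided Fisher test at 60+30 is 0.801, so 90 patients for power 0.80 reproduces.
- 90/(186/225) = 108.9 (plan: 111). 111/0.85 = 130.6 (plan: 132, as 88+44).
- Expected enrolment >10 mm: 88 × 186/225 = 72.7 and 44 × 186/225 = 36.4, about 73+36. With no loss, power is 0.87.

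**Who the unoperated arm A patients are**
- All sizes: 80/83 = 96.4% benign.
- For nodules >10 mm the protocol does not give the number of false negatives (FN), so FN is run from 0 to 3. Then FP = 75 − FN, TN = 136 − FP and the unoperated number U = TN + FN, which is 61 to 67 of 186. Benign share: 95.5% to 100%.

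**Complete-case failure rate in arm A** if a share f of the unoperated is lost and nobody else:

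rate = [FP + FN(1 − f)] / (186 − f·U)

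With FN = 0:
- f = 0.15: 75/(186 − 9.15) = 42.4%.
- f = 0.30: 75/(186 − 18.3) = 44.7%.
- All of the 15% arm A allowance: 0.15 × 186 = 27.9 lost, 75/158.1 = 47.4%. With FN = 3 this is 46.7%.

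| Loss (arm A unoperated only) | Arm A rate | Difference (points) | Evaluable A+B | Exact power |
|---|---|---|---|---|
| none | 40.3% | 32.8 | 73+36 | 0.87 |
| 15% of the unoperated | 42.4% | 30.7 | 69+36 | 0.81 |
| 30% of the unoperated | 44.7% | 28.4 | 65 or 66+36 | 0.74–0.76 |
| 15% of arm A, all unoperated | 46.7–47.4% | 25.7–26.5 | 62+36 | 0.64–0.66 |

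The same 62+36 reached by random loss would keep power at 0.86, so the fall in the last row comes almost wholly from the shift in the rate. That row needs 0.15 × 88 = 13.2 of about 32 unoperated patients to be lost, or 41% (42% to 46% in the >10 mm split).

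**The opposite bias in arm B.** If a share q of controls goes unoperated regardless of histology, the rate in all randomised controls is 0.731(1 − q) + 0.269q. Dropping those patients leaves 0.731, an overstatement of 0.462q: 2.3 points at q = 5%, 4.6 at 10%. The 2.1-point shift in the second row (42.4 − 40.3) is cancelled at q = 2.1/46.2, about 4.5%.

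**What keeping everyone would give** at 15% of the unoperated lost:
- All counted beneficial: arm A 40.1–40.3%, difference 32.8–33.0 points.
- All counted unbeneficial: (75 + 9.15)/186 = 45.2% at FN = 0, 45.5% at FN = 3; difference 27.6–27.9 points.

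**The case against.** The best defence is that dropping is an inference. Section 10.1 spells out one consequence of its rule, a reduced subset for multivariate models, and does not say that a patient without a 12-month ultrasound leaves the primary comparison. Section 8.3.4 could class such a patient as benign by default, and Section 8.6 has the file opened at 12 months anyway. Section 4.4 also explains intention-to-treat only as analysis by allocated arm, which dropping does not breach. This stands in part: the protocol contains the material for a sound rule. But its one explicit statement on missing values points the other way and makes no exception for the primary endpoint. A comparison that omits randomised patients by outcome-related loss is also not what intention-to-treat is meant to protect.

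A second defence is that missing-data detail belongs in the analysis plan. That would hold if the protocol were silent, but it fixes a rule.

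A third is that the arm A bias works against PET and so cannot create a false benefit. That is true of arm A alone. It is not true of dropped controls.

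A reader might infer more: that only unoperated arm A patients can lack an endpoint, so the effect must shrink and the planned power must be lost. The documents do not support this. Sections 8.3.5, 8.4 and 8.5 leave room for patients in either arm without histology, and at 15% of the unoperated lost the power still meets 0.80.

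**Conclusion.** The point holds in limited form. Section 10.1, applied as written, turns the primary analysis into a complete-case comparison. It sits badly with Sections 8.1.1, 8.3.4, 8.5 and 8.6, and the equal 15% inflation does not repair the consequence.

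The size depends on a loss rate that the protocol does not give for this group. It runs from about 2 points, with power still 0.81, at a loss of 15% of the unoperated arm A patients, to about 6 to 7 points, with power about 0.64 to 0.66, if they absorb the whole arm A allowance. The latter is a bound and not an expectation. All these figures assume no loss elsewhere and the protocol's own rates. Unoperated controls who are dropped would offset or reverse the shift, so net shrinkage is likely but not certain.

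It is worth correcting because it touches the primary estimate and the cost per unbeneficial treatment avoided. It does not invalidate the design.

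**What to change.** Amend Section 10.1 so that the no-completion rule does not apply to the primary endpoint, and keep every randomised patient with a nodule >10 mm in the primary analysis. Where neither histology nor the 12-month ultrasound is available, in either arm, classify the patient from the 12-month file review of Section 8.6 under the definition in Section 8.3.4. Add two bounding analyses, one counting all such patients as benign and one counting all as malignant, and report their number by arm.

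The cost is one rule and two sensitivity analyses on files that will be opened anyway, with no new visits. The Section 4.5 addendum reports recruitment complete at 132, so this is a change to the analysis and not to the sample size. It should be fixed before outcomes are compared by arm. The downside is that a missed cancer may be classed as benign; the bounding analyses show how much that could matter.
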